1.3.2 Primary Objectives

- To measure how the diversity and relative abundance of the nasopharyngeal resistome of children hospitalised with pneumonia differs from the nasopharyngeal resistome of healthy children in the community.
- To measure how the diversity and relative abundance of the nasopharyngeal resistome of children hospitalised with pneumonia differs from the nasopharyngeal resistome of children with pneumonia treated with antibiotics in the community.
- Investigate whether there is measurable persistence of a hospital-acquired nasopharyngeal
 resistome post-discharge, and whether this is associated with adverse health outcomes,
 including recurrent hospitalisation.

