Age, gender, co-morbidities, mid-upper arm circumference, pneumococcal vaccination status, antibiotics received 7 days prior to recruitment, haemoglobin level and malaria screening results will be recorded for all participants at recruitment; exposure to tobacco smoke from a household contact and whether the participant was breastfed in their first 3 months of life will also be recorded, as these are independently associated with pneumonia requiring hospitalisation in high-income settings [21]. Mode of childbirth (vaginal versus caesarean section) will also be recorded, as this influences early NPM development, and may be associated with childhood respiratory health [22]. To assess for acquisition of MGEs from the hospital environment, we will record data on duration of hospitalization and incidence of shared bed-spaces for hospitalised study participants, including number of occupants and number of days in a shared bed-space. Shared hospital bed-spaces will be sampled using a swab for metagenomic sequencing. Groups undergoing repeat NPS at 3 months will have health outcomes (including mortality), healthcare interactions (including healthcare facility and hospital attendance/admission) and antibiotic exposure recorded.

Groups being admitted to hospital will have WHO markers of severity in pneumonia recorded, including presence of the following at the time of admission: central cyanosis, oxygen saturations less than 90%, inability to feed, vomiting, convulsions, lethargy and impaired consciousness. To assess for potential influence of healthcare seeking behaviour on hospital re-admission, groups presenting to healthcare clinics and/or hospitals with pneumonia will have the educational level of the parents recorded, and the distance travelled to the healthcare clinic.

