2.9.1 Primary analysis

Participants will be gender-matched across groups. To establish differences in NPR composition the mean NPR diversity in a sample (measured using the Shannon index), mean relative abundance of all ARGs in a sample and mean relative abundance of specific ARGs in a sample will be compared between study groups using unadjusted t-tests, as summarised in Figure 4. Statistical analysis will be performed in R. Results will be presented in tables and illustrative heatmaps.

[figure not shown]

Figure 4. Plan for statistical analysis of NPR composition.

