2.9.2 Secondary analyses

Principal component analyses and non-metric multidimensional scaling will be used to determine whether there is a distinct hospital-acquired NPR in hospitalised participants. Conditional logistic regression will be used to test for association between NPR composition and re-hospitalisation with pneumonia within a 3-month period, controlling for potential confounders including co-morbidities, nutritional status, duration of hospital admission and severity of pneumonia.

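### The primary between-group comparisons for objectives 1 and 2 are fixed as unadjusted t-tests with matching on gender only, although the groups are not randomised and the protocol itself names possible confounders

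*Protocol*

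**What the plan says.** Section 1.3.2 sets two between-group primary objectives. The first measures how the resistome of hospitalised children "differs from the nasopharyngeal resistome of healthy children in the community". The second makes the same comparison with "children with pneumonia treated with antibiotics in the community". Section 1.3.1 puts the overall question causally: whether admission and antibiotic treatment generate a persistent hospital-acquired resistome. Section 1.1 wants to separate the effect of antibiotics from that of admission, with prescribing and admission policy in view.

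Section 2.9.1 gives one design control, "Participants will be gender-matched across groups", and one method: the Shannon index and the abundance measures "will be compared between study groups using unadjusted t-tests, as summarised in Figure 4".

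Section 2.1 records household tobacco smoke and breastfeeding in the first 3 months because "these are independently associated with pneumonia requiring hospitalisation in high-income settings". It records mode of birth "as this influences early NPM development, and may be associated with childhood respiratory health". Age, mid-upper arm circumference (MUAC), pneumococcal vaccination, co-morbidities and antibiotics in the previous 7 days are also recorded for every child. Section 2.4 says that the nasopharyngeal microbiome and resistome vary with season, and that community children are recruited before hospital children.

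The only adjustment stated is in section 2.9.2, for the secondary re-hospitalisation regression: "controlling for potential confounders including co-morbidities, nutritional status, duration of hospital admission and severity of pneumonia".

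**The concern.** Children admitted with pneumonia may differ from healthy or clinic-treated children in feeding history, smoke exposure, nutrition, vaccination and season of sampling. If any of these also relates to the resistome, an unadjusted difference in means mixes it with the effect of admission and antibiotics, and a larger sample does not remove it. The result could then be taken as evidence of a hospital-acquired resistome, or a real one could be masked. The adjusted model in section 2.9.2 does not help here. It compares re-admitted with not re-admitted children, and the confounders it lists do not include smoke, breastfeeding, mode of birth or season.

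**Working it through.** **1. The plan's own figure (section 2.5).** Inputs: Δ = 0.505 in SD units, two-sided 5%, 90% power.

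n = 2(Z₁₋α/2 + Z₁₋β)²/Δ² = 2(1.960 + 1.282)²/0.505² = 82.40, rounded up to 83 per group. This reproduces the stated 83. Power at 83 is 90.2% by the normal approximation and 89.9% by the noncentral t. The group sizes 83 + 92 + 92 + 83 sum to the stated 350. The calculation is sound for an unadjusted test; the issue is bias, not sample size.

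**2. Illustration of bias.** The protocol gives neither the imbalance of any host factor between groups nor its effect on the resistome, so both are assumed here. For one omitted binary factor:

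- bias (SD) = difference in prevalence × effect of the factor (SD)
- standard error of the group difference = √(2/83) = 0.155 SD
- false-positive rate = P(|Z + bias/0.155| > 1.96)

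| Prevalence difference | Effect 0.3 SD | Effect 0.5 SD | Effect 0.8 SD |
|---|---|---|---|
| 10 points | 0.03 SD: 5.4% | 0.05 SD: 6.2% | 0.08 SD: 8.1% |
| 20 points | 0.06 SD: 6.7% | 0.10 SD: 9.9% | 0.16 SD: 17.8% |
| 30 points | 0.09 SD: 8.9% | 0.15 SD: 16.2% | 0.24 SD: 34.0% |

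The bias runs from 6% (0.03/0.505) to 48% (0.24/0.505) of the design effect. The noncentral t gives nearly the same rates: 9.8% at 0.10 SD and 16.1% at 0.15 SD.

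If the bias opposes a true effect of 0.505 SD, power by the noncentral t falls from 89.9% to 83.0% (net effect 0.455), 73.7% (0.405) or 62.3% (0.355), for a bias of 0.05, 0.10 or 0.15 SD.

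**3. Price of adjusting.** Adjustment multiplies the required n by f = (1 − R²outcome)/(1 − R²group). R²outcome is the share of outcome variance explained by the covariates, and R²group the share of group membership. Both are assumed to lie between 0 and 0.20. Power at 83 per group:

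| R²outcome | R²group 0 | R²group 0.10 | R²group 0.20 |
|---|---|---|---|
| 0 | 90.2% | 87.0% | 82.9% |
| 0.10 | 92.9% | 90.2% | 86.6% |
| 0.20 | 95.3% | 93.2% | 90.2% |

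The n that keeps 90% power runs from 66 (82.40 × 0.80 = 65.9, rounded up) to about 103 (82.40 × 1.25) per group.

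**The case against.** - **Descriptive wording.** Section 1.3.2 asks how the resistomes differ. An unadjusted t-test answers that, and its 5% level is correct for the null of equal means. This stands. A reader might infer that the stated type I error is simply wrong; it fails only for the causal question of sections 1.1 and 1.3.1. Those sections, however, show how the contrasts are meant to be used.
- **No documented confounder among the host factors.** Smoke and breastfeeding are linked to hospitalised pneumonia, in high-income settings, but not to the resistome. Mode of birth is linked to the microbiome, and only tentatively to respiratory health. No reason is given for recording MUAC, vaccination or co-morbidity. A reader might infer that all of these are known to bias the result; the protocol does not support that. Season is better documented: section 2.4 ties it both to the resistome and to the order of recruitment.
- **Control already present.** Gender is the only matching variable but not the only control. Eligibility restricts age to 12-24 months and excludes HIV, immunosuppression, long-term antibiotics and, in these three groups, admission in the past six months. Section 2.3 also excludes severe anaemia from the study, although the list for healthy children in 2.7.3.2 does not repeat it. Healthy children come from wards near the hospital, and some healthy sampling continues over the following 6 months. All this reduces confounding. It does not balance feeding, smoke, nutrition or vaccination.
- **Within-child samples.** Hospitalised children are swabbed at the first visit, discharge and 3 months, and fixed host factors cancel in within-child change. Figure 4 is not available to this review and may contain such comparisons. They would not answer objectives 1 and 2, which are between groups.
- **A detailed plan is promised.** Section 2.9 calls its text a summary. But 2.9.1 is not silent: it states that the tests are unadjusted, so a later plan must either follow that or contradict it.

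**Conclusion.** The point holds as one about a stated method that does not suit the use made of it. For non-randomised contrasts that are to be read as the effect of admission and antibiotics, the protocol fixes an unadjusted primary comparison while collecting the covariates needed for a better one.

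The size of any bias is unknown. The false-positive range of 5.4% to 34% follows from assumed imbalances of 10 to 30 points and assumed effects of 0.3 to 0.8 SD. Its lower end is close to nominal, and nothing in the protocol says where in the range the study would fall. A reader might infer from the upper end that the primary results will be materially wrong; the documents do not support that. They support only that a host or seasonal difference could be read as a hospital effect, and that the planned analysis would not separate the two.

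**What to change.** In section 2.9.1, make the primary analysis for objectives 1 and 2 a linear regression of each resistome measure on group. Adjust for a prespecified set: age, sex, MUAC, pneumococcal vaccination, breastfeeding in the first 3 months, household smoke exposure, mode of birth, co-morbidity, and calendar season of sampling as far as the groups overlap in season. Report the unadjusted t-test as supportive. Use antibiotics in the 7 days before recruitment in a sensitivity analysis only, because antibiotic exposure is part of the question.

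No new data are needed: the host factors are already recorded for all children, and season follows from the sampling date. The unadjusted comparison of 83 with 83 has 2 × 83 − 2 = 164 residual degrees of freedom. Eight single terms plus three for season (if coded in quarters, an assumption) leave 153. The sample size was set for the unadjusted test, so power may move: about 83% to 95% at 83 per group under the assumed R² ranges, the low end arising if covariates explain 20% of group membership and none of the outcome.

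Two limits should be stated beside the model. Section 2.4 plans the later return visits for healthy children only, so seasonal overlap may be thin against community pneumonia. Section 2.1 records the WHO severity markers only in admitted children, so adjustment cannot remove differences in severity from that contrast.

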2.15.4 Challenges to identifying the legally acceptable representative for consent	
process	24
2.15.5 Failure of long read metagenomic sequencing	25
2.15.6 Reliable antibiotic consumption data	25
2.15.7 Global pandemic/Local epidemic	26
2.16 Future use of stored samples	26
2.17 Budget and finance	26
2.17.1 Budget justification	26

Version 5.0 21/05/2025

Executive Summary

Study type: This is a multi-site, extended observational case-control study with a preliminary cohort component.

Problem: Based on modelling, Sub-Saharan Africa is the region most affected by death due to antimicrobial resistance (AMR), but there is little AMR data from the region. Pneumonia remains a leading cause of death in children under 5 years old worldwide. To change this, we must understand how antibiotic selective pressure and healthcare exposure impacts AMR development and how AMR influences health outcomes in resource limited settings. The nasopharynx is a reservoir of organisms that cause pneumonia and their associated AMR. Metagenomic deep-sequencing enables identification of the nasopharyngeal resistome (NPR), all the genetic determinants of AMR within the nasopharyngeal bacterial niche. No study has examined whether human resistome composition is associated with health outcomes.

Objectives: Our study aims to answer the following research question; does hospital admission and antibiotic treatment for pneumonia generate a persistent hospital-acquired nasopharyngeal resistome in Malawian children, and is this associated with adverse health

 To measure how the diversity and relative abundance of the nasopharyngeal resistome of children hospitalised with pneumonia differs from the nasopharyngeal resistome of healthy children in the community.

outcomes in a resource limited setting? The primary objectives of this study are:

- To measure how the diversity and relative abundance of the nasopharyngeal resistome of children hospitalised with pneumonia differs from the nasopharyngeal resistome of children with pneumonia treated with antibiotics in the community.
- To investigate whether there is measurable persistence of a hospital-acquired nasopharyngeal resistome post-discharge, and whether this is associated with adverse health outcomes, including recurrent hospitalisation.

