2.0 Methodology

2.1 Study design

This is a multi-site, extended case-control study with a preliminary cohort component to assess the evolution of the NPR under selective pressure of antibiotic use and hospital admission for pneumonia in children aged 12-24 months in Malawi. The study will be led by the PhD student, [name], as a PhD fellowship.

NP Resistome Study

Version 5.0 21/05/2025

Page 10 of 30

In the preliminary cohort component, healthy children in the community will have a NPS collected at the first study visit, to determine the baseline community resistome through metagenomic sequencing (see Figure 1).

To assess the impact of oral antibiotics on the NPR, children presenting with pneumonia to community healthcare clinics, Ndirande and Gateway Primary Care Centre (GPCC), will have a NPS collected at the first study visit and 3-months post-recruitment, to determine the antibiotic-exposed resistome through metagenomic sequencing (see Figure 1).

To understand the impact of broad-spectrum intravenous antibiotics and exposure to a hospital environment on the NPR, children hospitalised with pneumonia (without any hospital admission 6 months prior) to Queen Elizabeth Central Hospital (QECH) will have a NPS collected at the first study visit, discharge and 3-months post-recruitment to determine a hospital-acquired resistome through metagenomic sequencing (see Figure 1).

[figure not shown]

Figure 1. Preliminary cohort component of the study. The yellow diamonds represent the key samples groups for NPR comparison.

The case-control component of the study will examine whether a hospital acquired NPR is associated with adverse health outcomes, specifically re-admission to hospital with pneumonia. Children hospitalised to QECH with pneumonia (without admission 6 months prior), who are not re-admitted within 3 months will form the control group (see Figure 2); these participants will have a NPS will be collected at the first study visit (within 24 hours of admission to hospital), discharge from hospital and 3-months post-recruitment to assess for a hospital-acquired resistome. Those hospitalised within the preceding 6 months will be

NP Resistome Study

Version 5.0 21/05/2025

Page 11 of 30

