2.4 Study period

This study will be conducted over a three-year period as a PhD fellowship, with participant recruitment over an 18-month period; see Figure 3. Due to the budget, our study team will not have the capacity to recruit in the community and hospital concurrently; community participants will be recruited prior to hospital participants.

We have chosen a 3-month follow up timepoint, to allow the resistome to return to a post-antibiotic baseline; a previous study demonstrated microbiome recovery within 3 months of infective-asthma exacerbation [23].

Importantly, there is evidence of seasonal variation in composition of the NPM and NPR [24]. Unfortunately, our study team size is restricted by budgetary constraints, therefore we are unable to recruit in the community and hospital simultaneously. We plan to conduct most of the community patient recruitment intensively within a 6-month period, before starting hospital recruitment. To restrict potential confounding due to seasonal effect, we plan to return to the community on an infrequent basis (approximately 3-4 weekly) for healthy community sampling over the following 6 months to ensure a baseline healthy resistome has been sampled across all seasons.

NP Resistome Study

Version 5.0 21/05/2025

Page 14 of 30

	December 2024 - February 2025	March - May 2025	June - August 2025	September - November 2025	December 2025 - February 2026	March - May 2026	June - August 2026	September - November 2026	December 2026 - February 2027	March - May 2027	June - August 2027
Set up study in-country											
Recruitment and data											
collection from COMMUNITY cohort											
Recruitment and data											
collection from											
HOSPITAL cohort DNA extraction and											
sequencing											
Bioinformatic pipeline											
optimisation											
Statistical analysis and thesis preparation											

Figure 3. Study timeline

Samples collected from study participants will be stored for 5 years after the conclusion of the study at Malawi Liverpool Wellcome program. The study will be completed within 18 months of the start of recruitment, or when the recruitment targets have been achieved and all samples collected (if this occurs in a time frame shorter than 18 months). Upon study completion, the Sponsor (LSTM), RECs and MLW will be notified; a report of the study findings will be submitted to COMREC, Blantyre district health office and LSTM.

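### The only primary test fixed for the resistome comparisons makes no use of antibiotics or admissions recorded before the 3-month swab, so fresh exposure can be mistaken for persistence if it is commoner in the hospital group

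*Protocol*

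**What the plan says.** - **Objective.** The Executive Summary, and section 1.3.2 in near-identical words, make this a primary objective: "To investigate whether there is measurable persistence of a hospital-acquired nasopharyngeal resistome post-discharge".
- **Sampling.** Under section 2.1 the hospital group has an "NPS collected at the first study visit, discharge and 3-months post-recruitment to determine a hospital-acquired resistome". The community pneumonia group is swabbed at recruitment and 3 months. Healthy children are swabbed once.
- **Timing.** Section 2.4 explains that 3 months was chosen "to allow the resistome to return to a post-antibiotic baseline".
- **Interim data.** For groups swabbed again at 3 months, section 2.1 has "healthcare interactions (including healthcare facility and hospital attendance/admission) and antibiotic exposure recorded".
- **Primary analysis.** Section 2.9.1 states that Shannon diversity, total resistance-gene abundance and abundance of specific genes "will be compared between study groups using unadjusted t-tests". It refers to Figure 4 for the contrasts, and that figure is not reproduced in the text available.
- **Secondary analyses.** Section 2.9.2 adds ordination methods with no stated adjustment. It also adds a conditional logistic model with re-hospitalisation as the outcome. The confounders that it names do not include interim antibiotics.
- **Re-admission.** In the case-control component (section 2.1), hospital children who return within 3 months are kept out of the control group. No matching rule is stated for the 3-month swab in the cohort component.

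**The concern.** A 3-month swab shows a return to baseline, or a failure to return, only in a child who has met nothing new in between. By the protocol's own hypothesis (section 1.2), antibiotics select resistance genes and the hospital environment adds mobile ones. A child who had another course or another admission before month 3 may therefore carry a newly selected or newly acquired resistome at the swab. That is re-acquisition, and an unadjusted comparison cannot tell it from persistence.

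What is at stake is the meaning of a positive 3-month result. If hospital children are re-exposed more often than their comparator, the study could report a lasting effect of the index admission when it has seen the effect of later treatment. Section 1.1 gives separating the effects of antibiotics and admission as a reason for the study. The data that would help to do so at 3 months are collected, but no stated analysis of that swab uses them.

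**Working it through.** **1. The protocol's own figure (section 2.5).** Inputs: standardised effect 0.505, two-sided 5% error, 90% power.

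n = 2(1.960 + 1.282)² / 0.505² = 82.4, rounded up to 83 per group. The stated 83 reproduces, and power at 83 per group is 90.2%.

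**2. False difference when nothing persists.** Let f be the proportion newly exposed in the hospital group minus that in the comparator. Assume that new exposure shifts the outcome by 0.505 SD and that children not re-exposed have fully recovered. Then:

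- bias = f × 0.505 SD
- standard error = √(2/83) = 0.155 SD
- rejection probability = Φ(bias/0.155 − 1.96) + Φ(−bias/0.155 − 1.96)

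| Excess exposure f | Bias (SD) | Rejection (nominal 5%) |
|---|---|---|
| 9 points | 0.05 | 6.0% |
| 10 points | 0.05 | 6.2% |
| 20 points | 0.10 | 10.0% |
| 30 points | 0.15 | 16.4% |
| 50 points | 0.25 | 37.0% |

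The exact noncentral t calculation gives nearly the same values (16.3% at 30 points, 36.6% at 50).

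**3. Where f could come from.**
- *Re-admission.* Section 2.15.1 borrows 18% over 6 months from severe anaemia. Half of that is 9% over 3 months, or about 8 of 92 hospital children. Even with no admissions in the comparator this is the 9-point row, so re-admission alone matters little.
- *Antibiotics.* The documents give no rate of interim use in either followed-up group. Section 2.15.6 cites 70% self-medication, but in rural adults, and it is not a difference between groups. The rows from 10 to 50 points are an assumed range.

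**4. Power of the alternatives, for a true 0.505 SD.**
- *Adjusted model.* Adding a binary exposure covariate inflates the variance by 1/(1 − R²), where R² is the squared correlation between group and exposure.

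| Exposed, hospital v comparator | R² | Inflation | Power at 83 per group | Evaluable per group for 90% |
|---|---|---|---|---|
| 30% v 10% | 0.062 | 1.067 | 88.3% | 88 |
| 40% v 20% | 0.048 | 1.050 | 88.8% | 87 |
| 50% v 20% | 0.099 | 1.110 | 87.0% | 92 |

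- *Restricted analysis.* Removing 30% of 83 hospital children leaves 58 v 83 and 83.4% power. Removing 50% leaves 41 v 83 and 74.7% power (noncentral t).

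**The case against.** **The contrast is not visible.** Figure 4 is not shown, so it is an inference that persistence is judged by a between-group t-test on the 3-month swab. The hospital group also has a discharge swab, and a within-group comparison is possible. This limits how firmly the exact contrast can be described. It does not remove the point, because none of the analyses that are described uses the interim records for that swab, and a discharge-to-3-month comparison would have no comparator to offset new exposure.

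**The detail belongs in the analysis plan.** Section 2.9 calls its text a summary and promises a fuller plan, which may add adjusted or sensitivity analyses. That is fair, and an unadjusted primary test does not bar them. But the protocol positively chooses unadjusted tests for the primary analysis, and the point is confined to what that choice can support.

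**Exposure may cancel.** It would largely cancel if equally common in the comparator. Community pneumonia children are followed to 3 months with the same records. Healthy children are not excluded for recent short courses. This stands: the bias depends on the difference between groups. Cancellation of admissions is less likely against healthy children, who must have had none in the past six months.

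**A reader might infer that re-exposure is bound to be counted as persistence, or that the 70% self-medication figure bounds the error.** The documents support neither. The first needs unequal exposure, which nobody has measured. The second would need almost no antibiotic use in the comparator, although the figure itself describes community use. The 0.505 SD effect is also a stand-in: section 2.5 takes it from one macrolide gene 3.5 years after mass azithromycin, not from a single interim course.

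**Adjustment can mislead too.** Section 1.2 supposes that a high-risk resistome goes with re-admission. Interim events may then be consequences of persistence, and adjusting for or excluding them could remove the very children in whom it persisted. This stands, and it is why the adjusted result should not replace the unadjusted one.

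**Conclusion.** The point holds in a limited form. Persistence is a primary objective, the 3-month time point presumes recovery from antibiotics, and interim exposure is recorded. Yet the fixed primary test cannot use that record, and no other stated analysis of the 3-month swab does. A positive result could therefore reflect later exposure rather than the index admission.

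The size is conditional. It assumes no true persistence, a 0.505 SD effect of new exposure, 83 per group, and excess exposure in the hospital group. Under those assumptions the error rate runs from about 6% at 10 points to 37% at 50 points. Re-admission alone accounts for about one percentage point above the nominal 5%, so the concern is mainly about antibiotics. It would be wrong to say that admissions go wholly unhandled, since the case-control component removes re-admitted children from its controls; that gap lies only in the cohort component.

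**What to change.** In section 2.9.1, or in the detailed analysis plan with a pointer from 2.9.1, before any 3-month results are seen:

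1. Keep the unadjusted 3-month difference and label it the net 3-month state.
2. Beside it, for the hospital and community pneumonia groups, specify a linear model of the 3-month swab with group, interim antibiotic course, interim admission and baseline covariates. Include severity only where it is recorded in both groups: section 2.1 requires the WHO severity markers only for groups being admitted.
3. Define an interim course as one beyond treatment of the index episode, because every child in both groups is prescribed antibiotics at entry.
4. Add a sensitivity analysis restricted to children not re-exposed. For the healthy comparator, which has one swab and no interval record, use only the restriction of the hospital children.
5. State that persistence will be attributed to the index admission only if these analyses agree with the unadjusted result.

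No new visits or data are needed. At 83 per group, power for 0.505 SD falls from 90% to about 87% to 89% in the adjusted model, and to 83% (58 v 83) or 75% (41 v 83) in the restricted one. Because interim events may follow from a persistent resistome, the adjusted and restricted results are supportive only.
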